6.4 Missing Data

Missing data will be quantified per variable (%), with missing data patterns noted through summarization by centre and compared by treatment group.

For primary effectiveness analysis, missing values will not be imputed given that the trial never reached complete enrolment.

6.5 Data Monitoring

6.5.1 Practical Measures to Minimise Bias

Clinical monitoring will be conducted according to Good Clinical Practise and Clinical Monitoring Plan. Furthermore, the Data Management Plan describes study specific processes for data review and handling, describing the strategy to review data for omissions, inaccuracies and inconsistencies.

Adverse event review and handling (SOP5-016 Rev 4 Clinical Trial Adverse Event Review And Handling) defines the process to protect safety of subjects and ensure the integrity of the safety data.

The results of unblinded interim analyses – both efficacy and safety -- will be available only to members of the DMC for decision making. Reports will also be provided for government authorities with oversight regarding conduct of clinical trials upon request. No information will be publicly available following interim analyses except for decision whether the trial is continued or discontinued.

6.5.2 Documentation of Interim Analyses

Documentation of interim analyses will be made according to Control Review and Approval of Clinical Trial Documents (SOP5-017). Data snapshot, programming, and reports will be preserved for the trial archive.

6.6 Multi-centre Studies

This is a multicentre study intended to be analysed as whole. Differences between sites are designed to be minimized by using it as a stratification factor. Individual centre results will be combined. Given that enrolment per centres may be small and there will be up to 70 centres, no adjustment for centres will be made for primary efficacy analyses. Treatment-by-centre interactions will only be tested as an exploratory analysis if a single centre contributes >10% of the patients in total analyses population. In this particular case, treatment will be considered as a fixed effect and the centre as a random effect.

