4.3 Randomisation and Blinding

Randomization will be applied using an internet based Interactive Web Response Systems (IWRS). In the trial, randomization will be done using random permuted blocks (based on procedure outlined in Pocock SJ. Clinical Trials: A Practical Approach. Wiley, Chichester, 1983), stratified by site, with 1:1 allocation ratio using a randomization list. At randomization, inclusion and exclusion criteria will be verified, and confirmation of informed consent signature will be done.

While investigator and subject will not be blinded to treatment group, all cMR analyses that provide value for the endpoint will be performed by a core laboratory which will be blinded to all clinical data including treatment group.

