12 lead ECG	X										
Adverse Events		X	X	X	X	X	X	X	X	X	
Catheter Access Site Assessment						X	X	X			
Cardiac Magnetic Resonance (cMR) imaging								X			
NYHA Assessment									X	X	
KCCQ Assessment									X	X	

COPY

5 Sample Size

Sample size considerations are based on both the primary effectiveness analysis.

The primary effectiveness analyses is designed to detect a relative reduction of 20% in mean anterior myocardial infarct size (IS), as determined by Cardiac Magnetic Resonance (cMR) imaging at 4-6 days post infarct in the Test Arm (cooling + PCI) compared to the Control Arm (PCI only). The absolute magnitude of a relative reduction of 20% depends on the mean IS in the control arm, which is assumed to be approximately 17 %LV. Therefore, the treatment effect of interest is an absolute difference of 3.5 %LV. Therefore, the treatment effect of interest is an absolute difference of 3.5 %LV.

The null hypothesis is that the mean IS in the Test Arm is equal to the mean IS in the Control Arm. The assumed standard deviation is 12 %LV and the final analysis will be conducted using a two-sided test at the alpha=0.044 level of significance (adjusted for the two interim analyses). Based on these assumptions, the required total sample to detect a mean difference of 3.5 %LV with 80% power is 384 subjects (192 subjects per group). Allowing for a potential dropout rate of 24%, the planned total sample size is 500 subjects (250 subjects per group).

$$H_0: \mu_T = \mu_C$$

$$H_A: \mu_T \neq \mu_C$$

Null hypothesis:

The null hypothesis is that the mean IS in the Test Arm is equal to the mean IS in the Control Arm.

Alternative hypothesis:

The mean %LV in the control arm is not equal to mean of control arm.

This 20% relative reduction is defined as absolute value 3.5 %LV and accounted for in our sample size calculation as treatment effect. This assumption is based on previous studies with anterior infarct size measured with cMR reporting between 17-20% absolute %LV in anterior infarct (**Tables 1 & 2**). Therefore, a relative reduction of 20% can vary depending on the mean infarct size of the control arm. Assuming a representative mean infarct size of ~17% in controls, we assume absolute difference of 3.5 %LV is equivalent to 20% mean anterior infarct size would be an adequate detection limit for effect.

COPY

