8.1 Primary Efficacy Analysis

To evaluate anterior infarct size (%LV) in Control and Treatment Arm, summary statistics will be used; n, mean, standard deviation median, interquartile range, minimum, maximum will be reported. T-test (2-sided) or Wilcoxon rank-sum test (2-sided) will be used as appropriate to calculate p-value after evaluation for normality.

9 Safety Analyses

To summarize incidence of adverse events, summary for all site reported events will be conducted on patient basis on the safety analysis set. Specifically, each patient will be counted once for an event and any repetitions will be ignored; the denominator will be the sample population size. Summaries will be produced by treatment (Test vs. Control) as well as an “All Patients” column. 1-sided Chi-square test or Fisher’s-exact test will be used as appropriate depending on whether number of patients are fewer than 5, in which case Fisher’s exact test will be used.

Only deviations from the aforementioned analytical and summary approaches will be noted in the subsequent subsections of section 9.

The only summarized variable is MACE, which is also a composite endpoint.

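### Randomisation is stratified by site but the primary analysis ignores site: if sites differ, the test is valid but conservative, at a modest cost in precision

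*SAP*

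**What the plan says.** - SAP section 4.3: randomisation uses permuted blocks, "stratified by site, with 1:1 allocation ratio using a randomization list". Section 4.1 says the same.
- SAP section 6.6 gives the purpose of stratifying: "Differences between sites are designed to be minimized by using it as a stratification factor". It then gives a reason for leaving site out of the analysis, "Given that enrolment per centres may be small and there will be up to 70 centres", and concludes that "no adjustment for centres will be made for primary efficacy analyses".
- SAP section 8.1: for the primary p-value, "T-test (2-sided) or Wilcoxon rank-sum test (2-sided) will be used as appropriate". No covariate or stratum enters.
- Centre appears elsewhere only in exploratory work. Section 6.3 allows models with country or centre. Section 6.6 allows a treatment-by-centre test when one centre holds more than 10% of patients, and there centre is modelled as a random effect.
- SAP section 5: the sample size uses a "two-sided test at the alpha=0.044 level of significance". It states "The assumed standard deviation is 12 %LV", with no split into between-site and within-site parts.

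**The concern.** Blocking within site keeps the arms nearly balanced in each site, so most of the between-site variation cancels out of the treatment difference. An unadjusted two-sample test does not know this. Its standard error is built from the total variation, between-site part included. If sites differ in mean infarct size, the standard error is too large, the confidence interval too wide and the p-value too high on average.

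The reason given in section 6.6 does not settle the matter. Many small centres are a good reason not to spend up to 69 degrees of freedom on fixed centre effects. A random intercept needs one variance parameter, and the same section accepts centre as a random effect for its exploratory test. At stake is some precision on the primary endpoint, in a trial that section 6.4 says did not complete enrolment.

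**Working it through.** **Inputs from the SAP.** Difference 3.5 %LV, SD 12 %LV, two-sided alpha 0.044, power 80%, 384 evaluable, 500 randomised, 24% dropout (section 5); up to 70 centres (section 6.6). That is 500/70, about 7 randomised per site, and 384/70, about 5.5 evaluable.

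**Assumptions, not in the SAP.** Between-site ICC from 0 to 0.20; block size 4; site sizes either equal or skewed.

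**Step 1: reproduce the SAP's figure.** The SAP says the number needed to "detect a mean difference of 3.5 %LV with 80% power is 384 subjects (192 subjects per group").
n per arm = 2 × (12/3.5)² × (2.014 + 0.842)² = 192 after rounding up, so 384 in total. This agrees exactly. Power at 192 per arm is 80.1% (79.8% by the noncentral t). The formula uses the total SD and no site term, so it describes the unadjusted test.

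**Step 2: closed form with perfect balance within site.**
True SE of the difference = 12 × √(1 − ICC) × √(2/192). The t-test uses 12 × √(2/192) = 1.225.
Example at ICC 0.10: true SE = 11.38 × 0.1021 = 1.162.
- Actual type I error of the t-test = 2 × [1 − Φ(2.014 × 1.225/1.162)] = 0.034.
- Power unadjusted = Φ[(3.5 − 2.014 × 1.225)/1.162] = 81.3%.
- Power adjusted = Φ(3.5/1.162 − 2.014) = 84.1%.

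This is a best case for adjustment. Incomplete blocks and dropout at sites of about seven patients spoil the balance, so the simulation below is the better guide.

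**Step 3: simulation.** 500 randomised over 70 sites, with a loss of 1 − 384/500 = 23.2% so that about 384 remain; 4,000 replicates per setting. The Monte Carlo standard error is about 0.6 points for power, √(0.8 × 0.2/4000), and 0.003 for type I error. Each cell gives equal site sizes / skewed site sizes.

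| ICC | Power, t-test (%) | Power, fixed centre (%) | Power, random intercept (%) | Type I error, t-test | Type I error, random intercept |
|---|---|---|---|---|---|
| 0 | 79.6 / 79.4 | 76.4 / 76.8 | 79.8 / 79.8 | 0.041 / 0.043 | 0.043 / 0.043 |
| 0.02 | 79.4 / 80.7 | 77.2 / 78.7 | 79.7 / 81.3 | 0.043 / 0.045 | 0.044 / 0.046 |
| 0.05 | 78.9 / 80.3 | 77.6 / 79.6 | 80.2 / 81.6 | 0.044 / 0.043 | 0.048 / 0.047 |
| 0.10 | 80.7 / 80.9 | 80.8 / 81.2 | 82.7 / 83.6 | 0.041 / 0.037 | 0.047 / 0.045 |
| 0.20 | 81.1 / 81.9 | 84.4 / 85.3 | 85.9 / 87.0 | 0.031 / 0.027 | 0.048 / 0.041 |

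A further simulation with 24% dropout gave t-test type I error of 0.038 to 0.046 at ICC 0.05, 0.032 to 0.037 at 0.10 and 0.026 to 0.030 at 0.20. The random intercept gained about 1, 2.5 and 5 to 6 points of power there, with no loss at ICC 0.

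**Step 4: read the comparison.** Fixed centre effects lose about 3 points at ICC 0, 2 at 0.02 and 1 at 0.05, and break even near 0.10. The random intercept loses nothing at any ICC examined, and its type I error stays close to 0.044. The Wilcoxon option was not simulated; as specified, it also ignores site.

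**The case against.** The case for leaving the SAP alone has real substance.

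- **The size is unknown.** With no ICC in the document, the effect could be nil. A blinded core laboratory reads every scan (sections 4.3 and 9.3), which limits reader differences as a source of site variation, although case mix can still differ. This stands, and it is why only a range is given.
- **The choice was prespecified and reasoned.** Against fixed effects the reason is correct, as Step 4 shows. It does not reach a random intercept. Using a random centre effect in a conditional exploratory test does not oblige the sponsor to use one in the primary analysis, but it shows the method is acceptable to them.
- **Enrolment stopped early.** The achieved numbers are not given, and adjustment cannot make up for missing patients. With an assumed 250 randomised over 60 sites, power was about 50% unadjusted and 51 to 52% adjusted at ICC 0.05 to 0.10. With 120 over 40 sites it was about 24 to 27% against 27 to 28%. The shortfall therefore adds little weight to the point.
- **A mixed model relies on normal theory,** whereas section 8.1 keeps a rank test in reserve. This is a genuine cost, met by keeping the rank test as a sensitivity analysis.

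A reader might go further and infer that the trial loses power its sample size had counted on. Step 1 does not support that: 384 was derived from the total SD without any site term and gives 80% for the unadjusted test. What is forgone is extra precision.

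**Conclusion.** The mismatch between design and analysis is real, and its consequence is modest. If mean infarct size varies between sites, the unadjusted test is valid but conservative. At an assumed ICC of 0.05 its actual type I error is about 0.04 and a random intercept adds about 1 point of power. At 0.10 the figures are 0.032 to 0.041 and 2 to 3 points; at 0.20 they are 0.026 to 0.031 and 5 to 6 points. At ICC 0 there is no difference. These figures assume 70 small sites, blocks of 4, and near-full enrolment with 23 to 24% lost.

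A reader might also conclude that the primary p-values are simply wrong, or that the result is at risk of a false positive. Neither follows. Any error is in the conservative direction, it depends on an ICC the SAP does not give, and it is hard to tell from zero for ICC up to 0.05. This is an efficiency improvement, not a defect of validity.

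**What to change.** Before database lock:

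1. In section 6.6, replace the sentence excluding centre from the primary analysis. In section 8.1, replace the test with a linear mixed model of infarct size on arm with a random centre intercept. Report the adjusted mean difference and its confidence interval.
2. State the fallbacks in advance. If the centre variance is estimated as zero, the model reduces to the unadjusted comparison. If the model does not converge, pool small centres by country.
3. Keep the t-test or Wilcoxon test as a sensitivity analysis.

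The cost is a change of SAP wording, one extra model and a normal-theory assumption for the primary estimate. It needs no new data or patients.

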6.7 Multiple Testing

For this trial, there is only one primary effectiveness outcome with two interim analyses. Overall significance value is preserved for interim analyses with established stopping rules preserving the overall type 1 error rate of alpha for <0.05.

For primary and secondary safety analyses, given the number of statistical tests, adjustment for multiplicity is considered counterproductive for considerations of safety as there is no control of the type I error for a single hypothesis. Tests will be conducted using one-sided test at alpha 0.05 level of significance.

All other analyses will be conducted using two-sided tests at the alpha=0.05 level of significance.

7 Summary of Study Data

[figure not shown]
Data will be sorted by treatment and centre and structured with columns for Test and Control. Descriptive and efficacy figures and tables will be produced for ITT and PP population. All

continuous variables will be summarised using the following descriptive statistics: n (non-missing sample size), mean, standard deviation, median, maximum and minimum. The frequency and percentages (based on the non-missing sample size) of observed levels will be reported for all categorical measures. In general, all tables will be annotated with population size relevant to the table/treatment, including any missing observations.

7.1 Subject Disposition

Number screened and randomized will be recorded and tabulated in *Study Eligibility* CRF according to variable for eligible (yes/no) and reason for no enrolment. *Enrollment & Randomization* CRF will document randomization assignation in variable “Assigned Treatment Group” that will determine the number of patients in each treatment arm. Patients reached 4-6 day cMR follow-up, patients reaching 30 day follow-up, patients with 12 months follow-up, and patients reaching completion of study will be tabulated according to documentation for date and time of visit according to follow-up CRFs: *4-6 Day Follow-Up*, *30 Day Follow-Up*, and *12 Month Follow-Up*. Study exits and Lost to follow-up will be recorded on *Study Exit* CRF in free text field. Death will be recorded in the *Adverse Events* form.

An example of a skeleton CONSORT diagram is provided below for evaluation of efficacy:

7.2 Protocol Deviations

Major protocol deviations or violation include the following:

Subjects with deviations relating to eligibility will be considered in the ITT analyses set, but not the PP analyses set.

Subjects with the following deviations relating to protocol implementation will also be excluded in the PP analyses set but included in the ITT analyses set:

- No cMR follow-up at 4-6 days leading to no IS data available. Missing data will be treated according Section 6.
- cMR completed out of 10 day window leading to available of IS data.
- Repeat infarction prior to 4-6 day cMR

The summary statistics will be produced in accordance with section 6.

7.3 Demographic and Baseline Variables

Demographics and Baseline clinical characteristics: age, sex, height (cm), weight (kg), BMI, systolic blood pressure (mmHg), diastolic blood pressure (mmHg), heart rate (beats/min), respiration (breaths/min), tympanic temperature at baseline (degree Celcius), glucose (mmol/L), calcium (mmol/L), magnesium (mmol/L), creatinine (umol/L), alcohol usage(current/past), smoking history (current/past), and medical history: history of cardiovascular conditions, diabetes, hypertension, and dislipidemia.

Treatment parameters: door to randomization, door to balloon time, door to wire-crossing time, randomization to wire crossing, randomization to balloon, and total ischemic time.

The summary statistics will be produced in accordance with section 6.

7.4 Medical History and Co-morbidities

Cardiac and non-cardiac medical history and comorbidities will be recorded in *Medical History* portion of CRF with reference to time of condition.

In particular: presence of diabetes, hypertension, dislipidemia, and previously known multivessel coronary disease will be summarized.

7.5 Prior and Concurrent Medications

Concurrent medications will be recorded in *Anti-Shivering Medications* and *Medication & Fluid* CRF. Summary statistics will be produced in terms of usage or total dosage for antishivering management including buspirone and pethidine. Usage of DAPT medications administered prior to procedure will be reported. These medications include heparin, aspirin, prasugrel, ticagrelor, clopidogrel, bivalirudin, and glycoprotein IIB/IIIa.

7.6 Treatment Compliance

Assessment of treatment compliance including submission of 4-6 day cMR for both Control and Test patients and availability of IS for analyses. For Test patients, compliance is additionally assessed as number of patients who are Cooled, assessed through the *Initiation of Cooling* CRF, which notes date and time of cooling initiation and the variable indicating “Initiation of Cooling – Not Done”. Other

measurements of compliance include the adherence to DAPT protocol, which is recorded in the Medications CRF.

The summary statistics will be produced in accordance with section 6.

Substantial protocol compliance for inclusion into Per-Protocol population is defined as the following:

- Received assigned treatment
 - Test subjects with no interrupted or problematic cooling
- cMR completed with available IS data within window (10 days)
- No repeat infarction prior to 4-6 day cMR

8 Efficacy Analyses

Efficacy variable IS (LV%) will be listed by subject within study centre. Data will be summarised by treatment group. N, Mean, Standard Deviation, Minimum and Maximum will summarise continuous efficacy variables. Plan in handling missing data for missing IS are documented in Section 6.

All assumptions for regression models will be assessed by viewing plots of the residual values. Transformation will be applied as appropriate as necessary for exploratory analysis adjusted by covariates including ischemic time.

8.1 Primary Efficacy Analysis

To evaluate anterior infarct size (%LV) in Control and Treatment Arm, summary statistics will be used; n, mean, standard deviation median, interquartile range, minimum, maximum will be reported. T-test (2-sided) or Wilcoxon rank-sum test (2-sided) will be used as appropriate to calculate p-value after evaluation for normality.

9 Safety Analyses

To summarize incidence of adverse events, summary for all site reported events will be conducted on patient basis on the safety analysis set. Specifically, each patient will be counted once for an event and any repetitions will be ignored; the denominator will be the sample population size. Summaries will be produced by treatment (Test vs. Control) as well as an “All Patients” column. 1-sided Chi-square test or Fisher’s-exact test will be used as appropriate depending on whether number of patients are fewer than 5, in which case Fisher’s exact test will be used.

Only deviations from the aforementioned analytical and summary approaches will be noted in the subsequent subsections of section 9.

The only summarized variable is MACE, which is also a composite endpoint.

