2.1 Background

Coronary heart disease complicated by acute myocardial infarction (AMI) remains a leading cause of death and disability worldwide. AMI most commonly occurs when a coronary artery becomes occluded by thrombus following the rupture of an atherosclerotic plaque. Factors that may affect the size of the subsequent infarction include duration of ischemia, size of ischemic territory, collateral blood flow, and myocardial metabolic rate. Long-term sequelae of AMI include ventricular remodeling, loss of ventricular function, congestive heart failure, dysrhythmias, and sudden death.

Although major gains have been made in improving the outcome of patients suffering AMI, and early myocardial reperfusion with the use of thrombolytic therapy or primary percutaneous coronary intervention (PCI) are effective, morbidity and mortality remain substantial. This may be because restoration of blood flow to the ischemic myocardium can itself induce injury through myocardial “ischemia reperfusion injury” (IRI), which can be defined as that portion of the ischemia-reperfusion

continuum which is preventable by treatment initiated after restoration of blood flow¹. It has been proposed that 50% of the final infarct size may be a function of IRI¹.

Ischemia reperfusion injury is protean in its components, likely including free radical and reactive oxygen species, disordered vasculature, inflammatory injury, programmed cell death, and pathologic remodelling among others². Unfortunately, the cascading nature of these events challenge and, in the end, may defeat the single molecular target pharmacologic model. The long list of failed IRI pharmacologic agents includes antioxidants, calcium channel blockers, anti-inflammatory drugs, sodium hydrogen exchange inhibitors, among others, has led some to question the importance of reperfusion injury in the myocardium³.

Therapeutic hypothermia (TH) has been studied for many years as a potential therapy for ischemia and reperfusion^{4,5,6,7,8,9,10}. The past few years have seen development of a broad literature reporting both laboratory and clinical trials of mild post-reperfusion TH in the treatment of disease entities as diverse as acute cardiac arrest, stroke, and myocardial infarction, among others. Unlike single pharmacologic agents, TH has the potential to modify and ameliorate multiple pathways of injury.

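### The primary infarct-size test adjusts for no baseline covariate; it is valid, but gives up precision that a short pre-specified model could recover

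*SAP*

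**What the plan says.** Section 8.1 gives the whole primary efficacy analysis: descriptive statistics by arm, and then "T-test (2-sided) or Wilcoxon rank-sum test (2-sided) will be used as appropriate to calculate p-value after evaluation for normality". No covariate enters.

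Section 2.1 names what drives the outcome: "Factors that may affect the size of the subsequent infarction include duration of ischemia, size of ischemic territory, collateral blood flow, and myocardial metabolic rate". Section 7.3 lists age and sex among the baseline variables, and also the time intervals: "Treatment parameters: door to randomization, door to balloon time, door to wire-crossing time, randomization to wire crossing, randomization to balloon, and total ischemic time". The schedules in section 4.4 include a baseline 12-lead ECG and a baseline troponin (I or T).

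Covariates appear in three places, none of them the primary test:
- Section 6.3 has subgroup interaction models, and optional exploratory models followed by stepwise selection at p ≤ 0.05.
- Section 8 mentions adjustment only in an exploratory role: "Transformation will be applied as appropriate as necessary for exploratory analysis adjusted by covariates including ischemic time".
- Section 13 plans a table of covariate associations and plots of infarct size against ischemic time.

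Section 6.6 gives a reason for not adjusting for centre (many small centres). No section gives a reason for leaving out patient-level covariates.

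The sample size in section 5 uses the raw spread of the outcome: "The assumed standard deviation is 12 %LV and the final analysis will be conducted using a two-sided test at the alpha=0.044 level of significance".

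**The concern.** In a two-sample comparison, all variation in infarct size between patients goes into the error term, including the part that baseline characteristics could predict. The SAP itself says that duration of ischemia matters, and it plans to plot and regress infarct size on ischemic time, yet the confirmatory test uses none of this information. Pre-specified adjustment for a prognostic baseline variable would narrow the confidence interval for the treatment difference and reduce the chance of missing a real effect. Section 6.4 states that enrolment was never completed, so precision can no longer be bought with more patients.

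This point is separate from adjustment for centre, and from the choice between t-test and Wilcoxon after inspecting normality.

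**Working it through.** **Inputs (SAP section 5).** Difference 3.5 %LV, SD 12 %LV, two-sided alpha 0.044, power 80%, 1:1 allocation (section 4.3).

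**Step 1: reproduce the plan's figure.** n per arm = 2 × SD² × (z₀.₉₇₈ + z₀.₈₀)² / difference² = 2 × 144 × (2.014 + 0.842)² / 12.25 = 191.7, so 192 per arm and 384 in total. This matches the SAP: "the required total sample to detect a mean difference of 3.5 %LV with 80% power is 384 subjects (192 subjects per group". The figure comes from the raw SD, so the design counts on no gain from covariates.

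**Step 2: effect of adjustment.** If pre-randomisation covariates explain a share R² of the outcome variance, then:
- residual SD = 12 × √(1 − R²)
- SE of the difference = residual SD × √(2/n)
- the SE falls by the proportion 1 − √(1 − R²), whatever the sample size
- the equivalent gain in evaluable patients is 1/(1 − R²) − 1

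The SAP gives no R², so the values below are assumptions. Power is from the noncentral t distribution, which gives 79.8% at 192 per arm; the normal approximation gives 80.1%.

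| Assumed R² | Residual SD | SE, 192 per arm | Fall in SE | Equivalent extra patients | Power, 192 per arm |
|---|---|---|---|---|---|
| 0 | 12.00 | 1.225 | – | – | 79.8% |
| 0.05 | 11.70 | 1.194 | 2.5% | 5% | 81.9% |
| 0.10 | 11.38 | 1.162 | 5.1% | 11% | 83.9% |
| 0.20 | 10.73 | 1.095 | 10.6% | 25% | 87.9% |

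At R² = 0.02, power is 80.6%, a gain of less than one point. Charging three degrees of freedom for the covariates changes power at 192 per arm by less than 0.01 percentage points.

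**Step 3: does the power gain grow if the trial stopped short?** The SAP does not give the attained number, so the smaller sizes are illustrative. For R² = 0.10:

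| Evaluable per arm | Unadjusted | Adjusted | Gain (points) |
|---|---|---|---|
| 192 | 79.8% | 83.9% | 4.1 |
| 100 | 51.5% | 55.9% | 4.4 |
| 50 | 28.4% | 31.1% | 2.7 |
| 25 | 15.9% | 17.2% | 1.3 |

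The proportional fall in SE is the same in every row. The gain in power is not.

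**Step 4: which covariates are available.**
- Age and sex are listed in section 7.3.
- Onset-to-randomisation time is not listed, but equals total ischemic time minus randomisation-to-balloon time if total ischemic time ends at the balloon. Section 7.3 does not define that end point.
- Troponin may be I or T, and no upper limit of normal is shown to be recorded for it.
- A baseline ECG is taken, but section 13 tabulates its findings as counts and percentages, and no quantified extent of ST elevation is shown.
- Total ischemic time, door-to-balloon time, TIMI flow after PCI and temperature at PCI are settled wholly or partly after randomisation and can be affected by cooling. They do not qualify.

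**The case against.** The strongest reply is that nothing here is an error. Randomisation makes the unadjusted comparison valid, and the 384 patients were sized for it with no covariate gain assumed. That stands. A reader might infer that the primary test is biased or that the trial is undersized for its own test; the documents support neither.

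Second, the benefit rests on an assumed R². Eligibility in section 4.2 narrows the spread of several prognostic factors (for randomised patients, anterior infarcts only; onset within 6 hours of presentation; no previous infarction; Killip class I only), so a low R² is plausible. That also stands, and it limits confidence in any one power figure. It does not affect the direction.

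Third, a reader might infer that the omission costs most because the trial stopped early. The step 3 figures do not show this: the power gain is about the same at 192 and 100 per arm and shrinks below that, and the attained number is not stated.

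Fourth, a reader might suppose that every obvious predictor is already in hand. Step 4 shows that this is not established for troponin and ST-elevation extent.

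Finally, changing the primary test at closeout of an open-label trial invites a charge of post-hoc model choice. The risk is real but can be managed. Section 2 places finalisation of the SAP before database lock, section 4.3 has the cMR core laboratory blinded to treatment group, section 6.5.1 restricts unblinded interim results to the DMC, and the unadjusted result would still be reported.

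**Conclusion.** The point holds as an inexpensive improvement in efficiency. Section 8.1 uses no baseline covariate, the SAP gives no reason for omitting patient-level ones, and its own background section says that at least one of them matters. For R² of 5, 10 or 20%, the standard error would be about 3, 5 or 11% smaller at any sample size, and power in the design case would be about 2, 4 or 8 points higher. These figures rest on the SAP's difference, SD and alpha, on the t-test branch of section 8.1, and on an R² that the SAP does not supply; if R² is near zero, almost nothing is gained. The omission and the direction of its effect are certain; the size is not.

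**What to change.** Before database lock, and by people without access to results by arm, amend section 8.1 as follows:

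1. Take the primary estimate and p-value from the treatment coefficient in a linear model of infarct size (%LV), with robust standard errors.
2. Name the covariates: age, sex and symptom-onset-to-randomisation time. Derive the last from the recorded times after confirming where total ischemic time ends.
3. Add baseline troponin or ST-elevation extent only if it is recorded in a comparable, quantified form.
4. Exclude total ischemic time, door-to-balloon time and every other post-randomisation variable, and do not use the stepwise selection of section 6.3.
5. Fill a missing baseline covariate with its overall mean.
6. Report the unadjusted difference as a sensitivity analysis.

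The cost is SAP wording, a few lines of code, a few degrees of freedom and a check on the recorded times. The main downside is a late change to the primary test, which must be documented as made before unblinded results were seen.
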